4.3 Design of the Trial

This Phase I multi-dose study will enroll a total of 12-15 subjects with documented critical limb ischemia (Appendix A). All subjects must meet inclusion and exclusion criteria as listed in Section 0. Each of 3 subjects in each of 4 cohorts will be evaluated as indicated following 2 IM doses of VM202 administered at 2-week intervals. Subjects in each of the four cohorts will all receive the same dose (2, 4, 8 or 16 mg) of VM202.

	Day															
	(-30) - (1)	1,15	30-37	39	69,84	99-106	108	138, 153	168-175	177	207, 222	237-245	365	434	503	572
Cohort I	Screen	Treat ment	Safety Review										End of Study			
Cohort II				Screen	Treat ment	Safety Review								End of Study		
Cohort III							Screen	Treat ment	Safety Review						End of Study	
Cohort											Treat	Safety				End of
IV										Screen	ment	Review				Study

Figure 4-1 Phase I Study Design

4.4 Dosing Cohort Assignment

A 3-digit subject number will be sequentially assigned to each study subject beginning with 101 when the informed consent is signed and any screening procedures are performed. Separate screening numbers will not be assigned. The subject will retain the original subject number assigned throughout the trial. If the subject is withdrawn from the study prior to receiving the first dose of study drug, that subject will be replaced but the subject number will not be reused.

A study pharmacist will be responsible to prepare the assigned study drug according to detailed instructions provided by the Sponsor or their designee.

4.5 Treatments

The test product used in this study is VM202, a plasmid DNA-based therapeutic product expressing HGF. The HGF gene, HGF-X7 is a genomic-cDNA hybrid HGF construct (HGF-X), which expresses both isoforms of HGF with high efficiency. VM202 has been developed using pCK DNA which has been safely used in previous human clinical trials with VEGF as the therapeutic vector. The VM202 plasmid, also identified as pCK-HGFX7 with 7377 base pairs, is composed of a HCMV enhancer/promoter, a growth hormone polyadenylation terminator sequence, ColE1 originator, and the Kanamycin resistance gene, on a pCK backbone.

For each of the 4 cohorts a different dose level will be administered as follows:

Cohort I- 2 mg of VM202

Cohort II- 4 mg of VM202

Cohort III-8 mg of VM202

Cohort IV-16 mg of VM202

In the event that a dose limiting toxicity (DLT) is determined after the safety review between Cohort I and Cohort II, between Cohort II and Cohort III or between Cohort III and Cohort IV, there will be 3 additional subjects treated at the same dose. If a DLT occurs in 2/6 patients, then the preceding dose level will be considered the MTD.

4.6 Duration

Each subject will be screened up to 30 days prior to receiving the first dose of study drug. Following screening, subjects will receive study drug on Day 1 and Day 15 and will be followed up until Day 365 post first dose of study medication. There will be safety evaluations that will begin 30 days after the first dose of study drug (Day 30) for all cohorts. Safety evaluations to encompass 30 days post the first dose of the first subject and subsequent to day 15 dosing of the other subjects in the same cohort will be completed for each cohort and will be evaluated by the DSMC prior to dose escalation to the next cohort. This 30-day window will include a 2-week safety evaluation following each dose at Day 1 and 15. The study will take approximately 30 months to complete. The individual subject enrollment will be approximately 12 months.

5.0 Selection and Withdrawal of Subjects

Subjects must meet the following inclusion and exclusion criteria in order to be enrolled into the study.

5.1 Cancer Screening

All subjects participating in this trial must undergo routine cancer screening. The history and diagnosis of potential, or apparent malignant, and non-malignant diseases and neoplasms will be assessed through several diagnostic tests and procedures. Some diagnostic tests and procedures performed prior to study consent and documented in the patient's medical history may be acceptable where noted. Routine cancer screening includes the following:

- 1. Current fecal occult blood test and flexible sigmoidoscopy within 5 years prior to treatment. Colonoscopy within cancer screening guidelines. Patients presenting with positive fecal occult will require flexible sigmoidoscopy during screening
- 2. Chest X-ray or CT scan of the chest (if the subject has a previous history of tobacco use, a CT scan will be performed instead of the chest X-ray) within 3 months prior to study entry
- 3. Mammogram (females only)-within 1 year prior to study entry
- 4. Papanicolaou (Pap) testing women within 1 year prior to study entry
- 5. Prostate specific antigen (PSA) men within 3 months prior to study entry
- 6. Current alpha-fetoprotein (AFP) will be performed at screening
- 7. CA-125 will be performed at screening (females only)

5.2 Inclusion Criteria

To participate in this study the subject must meet all of the following criteria:

- 1. Male or female, between 20 and 90 years of age
- 2. Have critical limb ischemia (Rutherford Class 4 and 5) and considered not a candidate for bypass graft surgery or percutaneous angioplasty due to comorbid conditions, failure of previous surgical or interventional procedures or caliber of grafting arteries

Critical limb ischemia is defined as:

- Stable symptoms on standard therapy including anti-platelet agents, vascular rheologic agents, cilostazol, anticoagulant and pain medication for 30 days
- Pain at rest and/or ischemic ulcers for a minimum of 4 weeks

- 3. Have diagnostic angiography of the affected limb in the last 12 months demonstrating a significant occlusion of one or more of the following arteries: iliac, superficial femoral, popliteal, and one or more infra-popliteal arteries
- 4. Have a resting ankle systolic pressure (in either the dorsalis pedis or posterior tibial arteries) of \leq 60 mmHg or a resting toe systolic pressure of \leq 40 mmHg in the affected limb
- 5. Be willing to maintain current drug therapy for peripheral arterial disease throughout the course of the study including an anti-platelet and statin (CoA Reductase) inhibitor treatment
- 6. Be capable of understanding and complying with the protocol and signing the informed consent document prior to being subjected to any study related procedures.
- 7. Women who are surgically sterile or at least 1 year postmenopausal or who have been practicing adequate contraception for at least 12 weeks prior to entering the study. If the subject is of child-bearing potential, she must have a negative serum pregnancy test result prior to study enrollment and must agree to repeat pregnancy screening tests during the study.
- 8. If the subject or the subject's partner(s) is of child bearing potential, the subject and the subject's partner(s) must agree to use a "double barrier" method of birth control while participating in this study.

5.3 Exclusion Criteria

To participate in this study a subject may not meet any of the following criteria:

- 1. Subjects who have undergone a revascularization procedure or sympathectomy within 12 weeks prior to study entry that remains patent. A failed revascularization procedure in the previous 4 weeks is acceptable.
- 2. Subjects with grade 3 (hemorrhages, exudates) or grade 4 (papilledema) retinopathy
- 3. Subjects currently receiving immunosuppressive medications, chemotherapy, radiation therapy
- 4. Subject with aorto-iliac occlusion (greater than 75%)
- 5. Subjects that will require amputation within 4 weeks of randomization
- 6. Subjects with any co-morbid conditions likely to interfere with assessment of safety or efficacy or with an estimated life expectancy of less than 6 months
- 7. Subjects with history of drug (defined as illicit drug use) or a history of alcohol abuse (defined as regular or daily consumption of more than 4 alcoholic drinks per day) within the past 3 months

- 8. Subjects with a current history or new screening finding of malignant neoplasm except for basal cell carcinoma of the skin and squamous cell carcinoma of the skin (if excised and no evidence of recurrence)
- 9. Subjects with evidence of active infection (e.g., cellulitis, osteomyelitis) or deep ulceration exposing bone or tendon in the extremity planned for treatment
- 10. Subjects with a clinically significant abnormality in routine hematology, urinalysis, chemistry, liver function or other laboratory tests, including HIV, Hepatitis B (HepBSAg), Cytomegalovirus (CMV), Hepatitis C Virus (HCV), Venereal Disease Research Laboratory test (VDRL), prostate-specific antigen (PSA) and chorio-embryonic antigen (CEA), or signs of malignant neoplasm by radiological imaging tests, including chest radiograph at Screening or Day 1.

Specific laboratory exclusion criteria include the following:

- Hemoglobin less than 9.0 G/dl
- WBC count less than 3,000
- Platelet count less than 75,000
- Fasting glucose greater than 250 mg/dl
- AST and/or ALT greater than 3x upper limit of normal
- 11. Subjects with any other condition that in the opinion of the Investigator might put the subject at risk or interfere with his/her participation
- 12. Subjects unwilling or unable to comply with the protocol or to cooperate fully with the Investigator or site personnel
- 13. Subjects that have received any other investigational drug within the 30 days prior to study drug administration or will receive such a drug during the timeframe of this study
- 14. Subjects with uncontrolled hypertension defined as systolic blood pressure greater than 200 mmHg or diastolic blood pressure greater than 115 mmHg at Baseline evaluation
- 15. Subjects with advanced liver disease including decompensated cirrhosis, jaundice, ascites or bleeding varices

5.4 Subject Withdrawal Criteria

Subjects will be discontinued from the study prematurely if any of the following occur:

- The subject requests to be withdrawn from the study
- The Principal Investigator decides that it is in the subject's best interest

- The subject requires percutaneous or surgical intervention for treatment of acute limb ischemia.
- The subject is noncompliant with the protocol

If a subject withdraws from the study at any time, either at his request or at the Principal Investigator's discretion, the reason(s) for withdrawal will be recorded by the Principal Investigator on the Case Report Form (CRF). If the subject withdraws after receiving any study drug, the subject will be encouraged to continue to be monitored after withdrawal. In this regard, they will be informed that it is in their best interest to return for all follow-up visits to monitor for possible delayed safety effects from the investigational therapy. If possible, all final visit tasks will be completed for all subjects who withdraw from the study. Subjects who withdraw prior to receiving the first dose of study drug will be replaced. Subjects who have received the first dose of the study agent will not be replaced. Subjects withdrawn due to AEs will be monitored until resolution of the AE, as described in Section 8.6.

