6.2.13 Early Termination Visits

Subjects who have had at least one dose of test material will return to the study site for study specific safety and efficacy assessment visits for the total study period (through Day 365), unless the subject withdraws study consent and refuses to participate. If the subject wishes to withdraw study consent, every effort must be made to encourage the subject to return to the study site for a termination visit assessment prior to withdrawing consent. The following procedures will be performed at the study termination visit:

- Chest X-ray or CT scan of the chest (if the subject has a previous history of tobacco use, a CT scan will be performed instead of the chest X-ray)
- Physical exam
- Vital signs
- Retinal fundoscopy
- Photograph and measurement of ulcer
- Clinical laboratory tests
- Infection tests
- Anti-HGF antibodies
- Endothelial progenitor cell assay
- High resolution MRA
- Hemodynamic assessments (ABI, TBI, Wave Form)
- Pain VAS

- TcPO₂
- Concomitant medications
- Adverse events

If a subject refuses to communicate with the study site, all attempts to contact the subject will be documented. The subject will be sent a certified letter to the subject's last known address.

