6.4.2 Replacement of Study Subjects

Subjects requiring percutaneous or surgical intervention for treatment of limb ischemia will be withdrawn from treatment. If the subject has received at least the first dose of study drug, the subject will not be replaced. If the subject has received one or both doses of study drug, the subject will remain in the study through the five year follow-up period.

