8.3 Handling Missing Data

Only data collected will be used for analysis. Missing values will not be imputed for this study.

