APPENDIX B: TABLE LAYOUTS

Viromed Co., Ltd. Page 1 of x Protocol Number: US-06-1-001

Table 1 **Subject Disposition** All Subjects

| | VM202- 2 mg | VM202- 4 mg | VM202-8 mg | VM202- 16 mg |
|--|-------------|-------------|------------|--------------|
| Subjects Enrolled | n | n | n | n |
| Safety Population [1] | n | n | n | n |
| ITT Population [2] | n | n | n | n |
| Received 2 Doses of VM202? | | | | |
| Yes | n (%) | n (%) | n (%) | n (%) |
| No | n (%) | n (%) | n (%) | n (%) |
| Last Visit Completed | | | | |
| Any Visit Prior to Visit- Day 21 | n (%) | n (%) | n (%) | n (%) |
| Visit- Day 21 | n (%) | n (%) | n (%) | n (%) |
| Visit- Day 28 | n (%) | n (%) | n (%) | n (%) |
| Visit- Day 59 | n (%) | n (%) | n (%) | n (%) |
| Visit- Day 91 | n (%) | n (%) | n (%) | n (%) |
| Visit- Day 180 | n (%) | n (%) | n (%) | n (%) |
| Visit- Day 365 | n (%) | n (%) | n (%) | n (%) |
| Completed Study? | | | | |
| Yes | n (%) | n (%) | n (%) | n (%) |
| No | n (%) | n (%) | n (%) | n (%) |
| Primary Reason for Discontinuation | | | | |
| Screen failure | n (%) | n (%) | n (%) | n (%) |
| Lost to Follow-up | n (%) | n (%) | n (%) | n (%) |
| Adverse Event | n (%) | n (%) | n (%) | n (%) |
| Non-compliance | n (%) | n (%) | n (%) | n (%) |
| Subject withdrew consent | n (%) | n (%) | n (%) | n (%) |
| Principal Investigator decision | n (%) | n (%) | n (%) | n (%) |
| Subject requires intervention for treatment of acute limb ischemia | n (%) | n (%) | n (%) | n (%) |
| Other | n (%) | n (%) | n (%) | n (%) |

^{*} Percentages based on number of subjects Enrolled.
[1] All subjects who received at least one dose of study drug.

^[2] All subjects who received at least one dose of study drug and had at least one post dose assessment.

Table 2
Demographic Characteristics
ITT Population

| | VM202- 2 mg (N=) | VM202- 4 mg (N=) | VM202- 8 mg (N=) | VM202- 16 mg (N=) |
|---|----------------------|----------------------|----------------------|-----------------------|
| Age (years) [1] | | | | |
| N | n | n | n | n |
| Mean (SD) | xx.x (xx.xx) | xx.x (xx.xx) | xx.x (xx.xx) | xx.x (xx.xx) |
| Median | XX.X | xx.x | XX.X | xx.x |
| Min, Max | xx, xx | xx, xx | xx, xx | xx, xx |
| Sex | | | | |
| Male | n (%) | n (%) | n (%) | n (%) |
| Female | n (%) | n (%) | n (%) | n (%) |
| Ethnicity | | | | |
| Hispanic or Latino | n (%) | n (%) | n (%) | n (%) |
| Not Hispanic or Latino | n (%) | n (%) | n (%) | n (%) |
| Race | | | | |

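### Protocol 5.4 ends study participation for acute limb intervention or non-compliance, while 6.4.2 and 6.2.13 keep dosed subjects in follow-up, so late data can be lost for reasons tied to outcome

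*Protocol*

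**What the plan says.** Protocol 5.4 (Subject Withdrawal Criteria) begins "Subjects will be discontinued from the study prematurely if any of the following occur". Two of its four triggers matter here: "The subject requires percutaneous or surgical intervention for treatment of acute limb ischemia" and "The subject is noncompliant with the protocol". No threshold for non-compliance is given. For what follows, the section says: "If the subject withdraws after receiving any study drug, the subject will be encouraged to continue to be monitored after withdrawal". Final-visit tasks are done where possible, and subjects already dosed are not replaced.

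Protocol 6.4.2 says: "Subjects requiring percutaneous or surgical intervention for treatment of limb ischemia will be withdrawn from treatment". It adds that a subject who has had one or both doses stays in the study.

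Protocol 6.2.13 says that subjects who have been dosed "will return to the study site for study specific safety and efficacy assessment visits for the total study period (through Day 365"), and the only exception it names is withdrawal of consent with refusal to take part.

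Protocol 6.6 keeps subjects in their visits to 12 months when the investigator stops test material for medical reasons. This supports 6.2.13, but it does not address the two triggers directly.

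In the SAP, Table 1 of Appendix B lists "Subject requires intervention for treatment of acute limb ischemia" and non-compliance among the primary reasons for discontinuation. SAP 8.3 says "Only data collected will be used for analysis" and rules out imputation.

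**The concern.** The same dosed subject falls under two rules. One ends study participation and makes later visits voluntary; the other keeps the visits as scheduled. Which rule a site applies decides whether late data exist for that subject.

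This matters because the exits are unlikely to be random. Intervention for acute limb ischemia reflects the state of the limb that the therapy is meant to help, and non-compliance may also be related to how a subject is doing. The endpoints run long: the first primary safety endpoint is adverse event incidence through Day 365, and hemodynamics, TcPO2, VAS pain and ulcer area are all assessed to Day 365 (Protocol 4.1). With observed data only, no replacement and three subjects per cohort, each such exit weighs heavily in its cohort.

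**Working it through.** **1. The rules side by side, for a subject who has been dosed**

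| Situation | 5.4 | 6.4.2 | 6.2.13 |
|---|---|---|---|
| Intervention for acute limb ischemia | Out of the study; monitoring encouraged | Out of treatment; stays in the study | Visits continue to Day 365 |
| Intervention for limb ischemia that is not acute | Not listed | Out of treatment; stays in the study | Visits continue to Day 365 |
| Non-compliance | Out of the study; monitoring encouraged | Not addressed | Visits continue to Day 365 |

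The first and third rows conflict. The second does not, because 5.4 is limited to acute limb ischemia. All three sections are current text, so the conflict does not rest on the amendment log. Section 6.4.2 still gives its horizon as five years, while the Synopsis and 4.6 give one year. Both reach Day 365, so this does not affect the point.

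**2. The plan's own sample size**

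4 cohorts × 3 subjects = 12; one cohort expanded by 3 after a dose-limiting toxicity gives 12 + 3 = 15. This reproduces the stated 12-15. The size is based on feasibility, so there is no power calculation to repeat.

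**3. What one exit removes**

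One of 3 is 33% of a cohort's later data, leaving n = 2. For a zero-event result, the exact one-sided 95% upper bound on the event rate is 1 − 0.05^(1/n):

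- n = 3: 1 − 0.05^(1/3) = 63.2%
- n = 2: 1 − 0.05^(1/2) = 77.6%
- n = 12, all cohorts together: 1 − 0.05^(1/12) = 22.1%

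The Safety population (SAP 5) is everyone dosed, so the printed denominator would stay at 3. For events after the exit, however, only 2 subjects would have been observed.

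**4. How often this could happen**

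The documents give no rate. Assume each subject independently has probability p of leaving under either trigger with no later data obtained. The chance that a three-subject cohort loses at least one is 1 − (1 − p)^3:

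- p = 10%: 27%
- p = 20%: 49%
- p = 30%: 66%
- p = 40%: 78%

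**5. Effect on a change-from-baseline mean**

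Let m be the mean change of the two who stay and w the change that the third would have shown. The mean of all three is (2m + w)/3, so losing the third shifts the mean by m − (2m + w)/3 = (m − w)/3.

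Take assumed VAS changes of −20 and −20 mm for those who stay. If w = +20, the full mean is −6.7 mm, the observed mean is −20.0 mm, and the shift is (−20 − 20)/3 = −13.3 mm, which looks better than the truth. If w is below −20, for instance because the procedure itself relieved pain, the shift is positive and the observed mean looks worse. The documents do not settle which case applies.

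**The case against.** The strongest reply is that this is a wording inconsistency with little practical effect. Much of that reply stands.

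- **Safeguards exist.** Section 6.4.4 expects vascular procedures during the study, requires each to be documented and asks sites to make every effort to bring the subject back. Section 6.2.12 encourages a return visit after such events, with VAS, TcPO2 and hemodynamics. The termination visit in 6.2.13 collects these plus ulcer measurement and MRA. Section 5.4 itself tells withdrawn subjects that returning is in their interest. Events before exit still count.
- **The consequence is limited.** Efficacy is descriptive and exploratory, every subject is listed, and the continuous efficacy tables print N at each visit. A missing subject would be visible, and neither alpha nor power is involved.
- **The direction of bias is open.** A reader might infer that late efficacy means must look better than they are. The documents do not support this: revascularization can itself improve hemodynamics, TcPO2 and pain. Retaining those values without marking them could also mislead.
- **The trigger is narrow.** A reader might infer that any limb intervention ends participation. Section 5.4 names acute limb ischemia only.
- **Table 1 is partly right already.** A reader might infer that it merges stopping treatment with leaving the study. It has separate blocks for receipt of two doses, last visit completed and study completion. What it lacks is a statement of what its discontinuation reasons refer to.

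The reply does not remove the conflict itself. Encouraged monitoring and a single termination visit are not the same as scheduled visits to Day 365.

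**Conclusion.** The concern holds as a contradiction in the current protocol with a possible, not certain, loss of late data. For a dosed subject with intervention for acute limb ischemia, 5.4 conflicts with both 6.4.2 and 6.2.13. For a non-compliant dosed subject, it conflicts with 6.2.13. Section 6.6 is supporting only.

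If 5.4 is followed and the subject does not return, one exit leaves 2 of 3 subjects in the cohort. The zero-event upper bound for the unobserved period then rises from 63.2% to 77.6%. The 27% to 78% chance of at least one such loss per cohort rests wholly on the assumed 10% to 40% range and on independence. The VAS figures are illustrative. No claim is made about the sign of the bias, and the study's feasibility-based size is unaffected.

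A reader might also conclude that follow-up should end only for withdrawn consent, loss to follow-up or death. That goes further than the conflict requires, because it would remove the investigator's best-interest exit in 5.4, which is not at issue here.

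The point should be fixed, but it does not undermine the design.

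**What to change.** 1. **Protocol 5.4.** Reconcile it with 6.2.13 and 6.4.2 by separating stopping treatment from ending study follow-up. For dosed subjects, limb intervention and non-compliance should not by themselves end scheduled data collection through Day 365. Leave the subject-request and investigator best-interest exits as they are.
2. **SAP Table 1.** Label the discontinuation block as discontinuation from study follow-up. Receipt of two doses already has its own block and needs no change.
3. **SAP listings.** Flag values collected after a limb intervention, using the intervention date that 6.4.4 already requires, so that a reader can judge them separately.

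This concerns data collection only, and no treatment rule is proposed. The cost is protocol wording, one table label and a listing flag. The visits are already in the schedule of assessments (Protocol Table 4-1).
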